#### **CONFIDENTIAL**

- Ability to contact patients at follow-up time points (e.g., number of phone calls required, whether participant appeared for the 6-month follow-up interview).

We may also examine for associations between participant characteristics and certain feasibility outcomes using bivariate and multivariable analyses as appropriate. For example, ability to contact participants and successfully complete the final study follow-up visit may be examined by number of phone numbers provided by the participant at baseline or by participant characteristics (e.g., type of substance use).

#### **10.4.3 Analysis of the Secondary Endpoint(s)**

Not applicable (there are not secondary endpoints).

#### **10.4.4 Safety Analyses**

Not applicable. AEs and SAEs will be recorded and reported as previously described.

#### **10.4.5 Adherence and Retention Analyses**

Adherence and retention are key components of our primary feasibility endpoints. These analyses are described in Section 10.4.2.

#### **10.4.6 Baseline Descriptive Statistics**

Simple descriptive statistics will be examined for baseline characteristics of study participants, as collected on the baseline study survey.

#### **10.4.7 Planned Interim Analysis**

Not applicable.

##### **10.4.7.1 Safety Review**

Not applicable.

##### **10.4.7.2 Efficacy Review**

Not applicable.

#### **10.4.8 Additional Sub-Group Analyses**

There are no planned sub-group analyses for this feasibility study. Any sub-group analyses conducted on the basis of experience with the trial will be purely exploratory in nature.

#### **10.4.9 Multiple Comparison/Multiplicity**

Not applicable.

#### **10.4.10 Tabulation of Individual Response Data**

All planned analyses use aggregate data. Individual data will not be published.

#### **10.4.11 Exploratory Analyses**

Planned exploratory analyses will include examining new onset homelessness as measured by entry into a homeless shelter within 6 months of the ED intervention (determined using the Department of Social Services CARES database), multiple self-reported housing status and substance use measures at the 6-month follow-up interview compared to baseline, and measures of health services use. Although we are not powering the study to show statistically significant effects on these outcomes, we will be able to determine feasibility of outcome measurement and gain a preliminary sense of potential intervention effects which may help in determining sample size and other design considerations for future larger studies. Additional exploratory analyses may be conducted based on stakeholder interests and feedback, including as determined during yearly stakeholder meetings.

CONFIDENTIAL

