- Via NYC governmental agencies (NYC Department of Social Services and/or NYC CIDI), review of CARES database (with consent of participants) for data on participants' homeless shelter use, including dates and types of shelter use prior and subsequent to study enrollment. NYC DSS—which administers the Homebase program to which we are referring participants as part of the intervention—has agreed to inform us of the outcomes of our referrals (either directly or via their contracted agencies), including whether the participants enter a homeless shelter, for participants who have provided consent. NYULH researchers will not be directly accessing outside databases.

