## **10 Statistical Considerations**

### **10.1 Statistical and Analytical Plans**

There will not be a formal SAP for this small feasibility pilot study.

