### **10.2 Statistical Hypotheses**

As the primary endpoints for this study are measures of feasibility that are descriptive in nature, there are no formal or testable null or alternative hypotheses. For exploratory endpoints of housing and substance use outcomes, we will test the hypothesis that participants will have improved in these outcome measures at the time of the 6-month follow-up survey compared to the baseline survey. However, as noted previously, the study is not being powered to formally test these hypotheses and, therefore, any such analyses will be considered purely exploratory in nature.

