### **10.3 Analysis Datasets**

A single analysis dataset will include all participants. The analysis dataset will consist of the following:

- Baseline and follow-up participant surveys and other study instruments.
- Participant locator form information.
- Information collected from follow-up/tracking phone calls and/or NYULH SendSafe emails with participants and/or applicable service providers, as previously described.
- Participant information extracted from approved external sources (with participant consent) including the Bellevue Hospital Center EMR and the NYC DHS CARES dataset.

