#### **10.4.2 Analysis of the Primary Efficacy Endpoint(s)**

There are not primary efficacy endpoints for this study. Rather, the primary endpoints are measures of intervention/study feasibility. The main analyses for feasibility will involve simple descriptive analyses examining endpoints including:

- Number of patients approached, number (percent) screening positive for unhealthy alcohol or drug use, number (percent) screening positive for homelessness risk.
- Number (percent) of those approached who are eligible for the study. Number (percent) reasons for ineligibility.
- Number (percent) of those eligible who agree to participate. Number (percent) reasons for refusal.
- Basic characteristics (e.g., gender, age, race, primary drug vs. alcohol use) of those who were eligible vs. ineligible and agreed and did not agree to participate using descriptive statistics and bivariate analysis.
- Number and location of referrals made for homelessness prevention and/or substance use services. Number and types of homelessness prevention and other services actually received. Length of time between the ED intervention and receipt of services.
- Participant satisfaction and self-efficacy measures as assessed at baseline and 6 month follow-up visits.

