## **10.5 Sample Size**

Our goal is to test the feasibility and acceptability of the intervention and study processes. We expect this goal can be accomplished by enrolling approximately 40 ED patients, which will allow us to try the intervention for a range of different types of patients and to encounter a wide array of issues to be considered for a future large trial. The enrollment goal of approximately 40 patients, which equates to 1–2 patients per week over 6 months, is feasible. As this is a feasibility study only—not a study meant to test outcome effects—further sample size calculations are unnecessary and would be inappropriate.

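### Six-month self-reported housing is a completers-only result that probably looks too good, and the plan never compares CARES shelter entry between those interviewed and those not

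*Combined protocol and SAP*

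**What the plan says.** Section 10.4.11 plans to examine "multiple self-reported housing status and substance use measures at the 6-month follow-up interview compared to baseline", together with shelter entry within 6 months from CARES and measures of health services use. Section 10.2 adds a hypothesis of improvement between the two surveys, with the caveat that "the study is not being powered to formally test these hypotheses". Section 10.4.2 lists among the primary feasibility measures "Participant satisfaction and self-efficacy measures as assessed at baseline and 6 month follow-up visits"; section 4.2.1 explains that satisfaction is asked in the ED straight after the intervention and again at the 6-month interview.

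Section 10.3 states: "A single analysis dataset will include all participants". Its contents include surveys, tracking data, the Bellevue record and CARES. Section 7.1.1 provides for "review of CARES database (with consent of participants"), supplied through city agencies, and section 13.5 limits this to people referred to Homebase who have consented. Section 2.3.2 has every participant referred.

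On loss to follow-up, section 10.4.2 offers one optional analysis: "ability to contact participants and successfully complete the final study follow-up visit may be examined by number of phone numbers provided" at baseline, or by participant characteristics, with type of substance use as the example. Section 10 contains no missing-data method, bounds or sensitivity analysis, and section 10.1 says: "There will not be a formal SAP for this small feasibility pilot study".

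**The concern.** A comparison of survey answers at baseline and 6 months can use only people with both surveys, whatever the analysis dataset contains. The protocol itself makes outcome-related loss plausible. Enrolment selects for homelessness risk (5.1), a telephone is required for entry (5.2), interim contact is mainly by phone (7.3.3), and some participants are expected to worsen during the study in a population with housing instability (8.1). A person who loses housing may be harder to reach and would then drop out of the very result that should record the loss. Section 5.6 lets unreached participants be replaced, which adds interviews without revealing what happened to those lost.

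Section 10.4.11 intends these results to inform the sample size and design of a larger trial and to show whether outcomes can be measured. Whether the interview misses people who enter shelter bears directly on the second aim. The plan will hold data that partly answer the question, and no analysis puts it to them.

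**Working it through.** **The plan's own figure.** Section 10.5 gives "approximately 40 patients, which equates to 1–2 patients per week over 6 months". Over 26 weeks, 1 to 2 per week is 26 to 52 patients, and 40/26 = 1.54 per week, so the figure reproduces. It sets N = 40 below. No power calculation applies.

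**Where each outcome comes from.**
- Self-reported housing and substance use at 6 months: interview only (4.2.3, 10.4.11).
- Satisfaction: in the ED at baseline, then at the 6-month interview (4.2.1).
- Shelter entry within 6 months: CARES, no interview needed (7.1.1, 10.4.11). Name, date of birth and, if applicable, SSN are collected at baseline for linkage (7.1.1).
- CARES split by interview completion: not planned anywhere in section 10.

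**Illustration 1: bounds.** The loss rate, event rate and ratio are all assumed.
- 10 of 40 lost, 3 of 30 completers homeless: reported 3/30 = 10%.
- Those lost have three times the rate (30%): (3 + 0.30 × 10)/40 = 6/40 = 15%.
- None or all of those lost homeless: 3/40 = 7.5% to 13/40 = 32.5%.
- With 6 lost and the same 3 cases: 3/40 to 9/40, or 7.5% to 22.5%. With 14 lost: 3/40 to 17/40, or 7.5% to 42.5%.

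These bounds use the survey alone. CARES would narrow them from below: if it showed shelter entry in 3 of the 10 lost, at least 6/40 = 15% would have lost housing at some time. The upper bound would stay, because CARES does not see other forms of housing loss.

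**Illustration 2: size of the bias.** Let p be the true proportion losing housing, and rL and rH the interview completion rates among those who lose and keep it. The rate among those interviewed is p·rL / [p·rL + (1 − p)·rH]. With p = 0.20, rL = 0.5 and rH = 0.9:
- Interviewed: 0.20 × 0.5 + 0.80 × 0.9 = 0.82, about 33 of 40.
- Rate among those interviewed: 0.10/0.82 = 12%, against a true 20%.
- Rate among those missed: 0.10/0.18 = 56%.

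Over assumed ranges of p from 10% to 30%, rH from 0.8 to 0.9 and rL from 0.3 to 0.6, the interview understates housing loss by about 2 to 18 percentage points. If rL = rH, the bias is zero.

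**Precision of the proposed table.** With 3/10 lost against 3/30 interviewed, exact 95% intervals are about 7% to 65% and 2% to 27% (two-sided Fisher p about 0.15). With 4/8 against 4/32 they are 16% to 84% and 4% to 29%. The table can only be descriptive.

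**The case against.** The strongest reply is that most of what is needed is already planned. CARES shelter entry is an exploratory outcome in its own right, does not depend on the interview, and sits in the all-participant dataset. What is missing is one cross-tabulation in a single-arm pilot of about 40, whose housing outcomes are declared exploratory. The protocol also works against loss: multiple contact numbers (5.4), permitted contact through case workers and treatment programmes (7.3.3), an interview window running to eight weeks late (7.3.4) and follow-up by telephone (15.3). Retention will be reported as a feasibility result, and 10.4.11 allows further exploratory analyses.

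This limits the point but does not remove it. Exploratory status excuses imprecision, not a selected comparison presented without saying so.

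Three stronger readings are tempting and go too far.
- A reader might infer that CARES covers everyone. It covers those who consent and can be linked. By design that should be all enrolled, but consent can be revoked (5.7.1) and linkage can fail.
- A reader might infer that CARES shows the outcome-related loss directly. It records shelter use only, so it misses street homelessness and doubling up, and it says nothing about substance use or satisfaction.
- A reader might infer that the results are certainly biased in the favourable direction. No contact rates by housing status are given, so for housing this is an inference that the table would test. For satisfaction, nothing in the documents links being lost to being less satisfied.

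Nor is the optional attrition analysis confined to baseline variables: its characteristics are examples. It simply does not name CARES or later housing status.

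**Conclusion.** The point holds in a limited form. The 6-month self-reported housing and substance use results, and 6-month satisfaction, are completers-only results. The housing comparison is likely, though not certain, to look too favourable. A planned data source that could partly show this is not used for the purpose.

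The size is unknown, because the documents give neither retention nor housing-loss rates; the figures above are assumptions, including a reported 10% that becomes 15% under a threefold rate in those lost. The direction rests on one inference: that losing housing lowers the chance of an interview.

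Satisfaction is affected only in its 6-month part, since ED ratings are taken at baseline. The counts of patients approached, eligible, consenting and referred are untouched. The change should be made before analysis because it is cheap and these results are meant to guide the next trial.

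**What to change.** 1. In 10.4.11, tabulate CARES shelter entry separately for interview completers and non-completers, descriptively, with exact confidence intervals. Use the fixed 6-month window for everyone, because interviews may fall two weeks early to eight weeks late. Make CARES in all consenting, linkable participants the lead housing result, report how many could not be linked, and note that it captures shelter entry only.
2. In 10.4.11, label the self-reported housing result as completers-only and give the range if none or all non-completers had lost housing.
3. In 10.4.2, show 6-month satisfaction beside the same people's baseline (ED) satisfaction, and the baseline satisfaction of those lost. Note that ED ratings precede any Homebase visit arising from the referral, so they cannot stand in for later satisfaction with Homebase, and that CARES cannot measure bias in satisfaction.

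The cost is analysis wording and a few extra table columns from data already to be collected, with no new visits and no change in sample size. The drawback is low precision at about 40 participants, which the text should state.

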## **10.5 Sample Size**

Our goal is to test the feasibility and acceptability of the intervention and study processes. We expect this goal can be accomplished by enrolling approximately 40 ED patients, which will allow us to try the intervention for a range of different types of patients and to encounter a wide array of issues to be considered for a future large trial. The enrollment goal of approximately 40 patients, which equates to 1–2 patients per week over 6 months, is feasible. As this is a feasibility study only—not a study meant to test outcome effects—further sample size calculations are unnecessary and would be inappropriate.

## **10.6 Measures to Minimize Bias**

### **10.6.1 Enrollment/Randomization/Masking Procedures**

Not applicable. This is a single-arm, non-randomized study; no blinding or masking is appropriate.

### **10.6.2 Evaluation of Success of Blinding**

Not applicable. The study is not blinded.

### **10.6.3 Breaking the Study Blind/Participant Code**

Not applicable. The study is not blinded.

## **11 Source Documents and Access to Source Data/Documents**

Source data is all information, original records of clinical findings, observations, or other activities in a clinical trial necessary for the reconstruction and evaluation of the trial. Source data are contained in source documents. Original paper documents for the current study include: signed study consent forms, study reimbursement receipts, study screening and survey assessments (paper forms include TLFs and WHO-ASSIST; other baseline and 6-month assessments will be maintained on REDCap), documentation of study contacts including follow-up phone calls.

For paper forms, all entries should be printed legibly in black ink. If any entry error has been made, to correct such an error, draw a single straight line through the incorrect entry and enter the correct data above it. All such changes must be initialed and dated. Do not erase or white out errors. For clarification of illegible or uncertain entries, print the clarification above the item, then initial and date it. For study information entered into REDCap, REDCap automatically keeps logs of all changes made in forms.

Access to study records will be limited to IRB-approved members of the study team. The investigator will permit study-related monitoring, audits, and inspections by the IRB/EC, the sponsor, government regulatory bodies, and University compliance and quality assurance groups of all study related documents (e.g. source documents, regulatory documents, data collection instruments, study data, etc.).

Participation as an investigator in this study implies acceptance of potential inspection by government regulatory authorities and applicable University compliance and quality assurance offices.

## **12 Quality Assurance and Quality Control**

Multiple steps will be taken toward quality assurance (QA) and quality control (QC).

- All study staff, including RAs and RC, will be thoroughly trained both in overall GCP and human subjects protections and in study-specific procedures.
  - Formal training will occur prior to the study beginning recruitment.
  - Continuous training will occur in weekly staff team meetings.
- RAs will be closely supervised by the RC, with PI oversight. The RC will be supervised by the PI.
- A SOP document will clearly outline all study procedures, including QA/QC procedures.
- Multiple QA/QC protections are built into REDCap data collection software being used for this study, including forced question entry (i.e., specified questions cannot be left blank), automatic logging of all activities in REDCap including any entry changes, and study staff permission rules.

CONFIDENTIAL

- All paper forms, including consent forms, will be regularly reviewed (both at the time of initial completion and at least weekly) for completeness.
- Weekly QA/QC reviews between the PI/RC will include:
  - Review of numbers of patients approached, eligible/ineligible, refused, participated.
  - Review to ensure that all eligibility classifications were made correctly.
  - Review for missing or out of range data.
  - Review of any potential QA/QC issues identified by any study staff member (which did not warrant more immediate discussion).

The PI and RC will oversee QA and QC efforts.

The investigational site will provide direct access to all trial related sites, source data/documents, and reports for the purpose of monitoring and auditing by the sponsor, and inspection by local and regulatory authorities.

## **13 Ethics/Protection of Human Subjects**

### **13.1 Ethical Standard**

The PI will ensure that this study is conducted in full conformity with Regulations for the Protection of Human Subjects of Research codified in 45 CFR Part 46.

### **13.2 Institutional Review Board**

The protocol, informed consent form(s), recruitment materials, and all participant materials will be submitted to the IRB for review and approval. Approval of both the protocol and the consent form will be obtained before any participant is enrolled. Any amendment to the protocol will require review and approval by the IRB before the changes are implemented to the study. All changes to the consent form will be IRB approved; a determination will be made regarding whether previously consented participants need to be re-consented.

### **13.3 Informed Consent Process**

In obtaining and documenting informed consent, the investigators will comply with applicable regulatory requirements in adherence to 45 CFR Part 46.

#### **13.3.1 Consent/Assent and Other Informational Documents Provided to Participants**

Consent forms describing in detail the study intervention, study procedures, and risks are given to the participant and written documentation of informed consent is required prior to starting intervention. The written consent form was developed using the IRB-approved template and includes all required components. In addition, participants will be given a Simplified Study Information Handout that explains the key points of the study in simple, easy to understand language. The following consent materials are submitted with this protocol: *ED-Home Informed Consent* and *ED-Home Key Information Sheet*.

#### **13.3.2 Consent Procedures and Documentation**

Eligible patients will be invited to complete the written informed consent process in the ED. Multiple steps will be taken to ensure participant privacy during the consent process, including: asking any visitors to leave the area; using a private room or treatment bay when available (many of the treatment areas in the ED are private rooms with doors that close or single-patient bays with curtains that close, but if the patient is not already in one of these locations patients can be moved to a more private area of the ED); research staff speaking in a quiet voice to avoid others overhearing the conversation. Informed consent is a process that is initiated prior to the individual's agreeing to participate in the study and continues throughout the individual's study participation. Extensive discussion of risks and possible benefits of participation will be provided to potential participants. An IRB-approved key information form and informed consent document will be provided to patients and will also be verbally explained by trained study staff (generally RC, though may include the PI) and will detail, in simple and plain language, all study procedures and potential risks of participating in the study. As part of the consent process, study staff will explain the purpose of the study,

CONFIDENTIAL

all study processes, risks and benefits of being in the study, alternatives to being in the study, what information will be collected from participants, and how that information will be used. The rights and welfare of the participants will be protected by emphasizing to them that the quality of their medical care will not be adversely affected if they decline to participate in this study.

Privacy will be assured by asking any visitors to leave the area (though visitors will be allowed to stay for the consent process if preferred by participants). When feasible, research staff will also offer to move participants to a more private/quiet location of the ED.

Participants will be invited to carefully review the full study informed consent document, and to ask any questions they might have. Potential participants will have the opportunity to discuss the study with their surrogates or think about it prior to agreeing to participate. The participant and the person obtaining informed consent will sign and date two copies of the informed consent document prior to any procedures being done specifically for the study. One copy of the signed informed consent document will be given to the participant for his/her records and the other signed copy will be stored with study research records in a locked file cabinet in a locked office. Any alteration to the standard consent process and the justification for such alteration will be documented.

Regular audits will be performed by the RC to ensure that consent forms are fully and properly completed and stored for all study participants.

*Participant capacity and comprehension:* Potential participants will be required to demonstrate adequate comprehension of the study and decision-making capacity to participate in the study. Only patients who have the capacity to give informed consent will be included in the study. Patients will not be included if they are too acutely intoxicated to give informed consent or otherwise medically unfit to participate, as determined by trained study staff or the ED care team. If there is any question about the patient's capacity to provide informed consent, study staff will: a) ask ED care providers (e.g., physician, nurse) for advice about whether the participant has capacity to provide consent, and/or b) complete formal assessment of decisional capacity for participation in research using the University of California, San Diego Brief Assessment of Capacity to Consent (UBACC). The UBACC has been previously validated and used for studies at Bellevue Hospital, and generally takes less than 5 minutes to administer.

